Study Plan

of a Non-Interventional Observational Study

Infusion of gelatine solutions in pediatric patients aged up to 12 years

GPS - Gelatine in Pediatric PatientS

Study ID No.: HC-O-H-1406

NCT02495285

Date: 13.03.2019

Marketing Authorisation Holder:

**B. Braun Melsungen AG
Germany**

Organized and Financed by:

**B. Braun Melsungen AG
Division Hospital Care
[name]
[name]
Germany**

STUDY OVERVIEW

Title	Infusion of gelatine solutions in pediatric patients aged up to 12 years Acronym: Gelatines in Pediatric patientS (GPS)
Product under investigation	Plasma volume replacement solutions containing gelatine (Gelaspan® 4% & Gelofusine® 4%)
Study design	Prospective, non-interventional, international, multicentric observational cohort study
Number of sites, countries	≥ 10 European centers (e.g., Austria, France, Germany, Italy)
Phase	Post-authorization, non-interventional, clinical study voluntarily performed by Marketing Authorization Holder (MAH)
Indication	Treatment of hypovolemia and shock
Primary objective and variable	To gain additional information (dosing used during different surgeries) during routine clinical practice when used in pediatric population
Secondary objectives and variables	
Further evaluation of safety and efficacy based on routinely measured clinical parameters:
 
Safety:
 
 • blood gas analysis (pH, HCO₃⁻, pCO₂, sO₂, BE, Hb, Hct, lactate, Na⁺, K⁺, Ca²⁺, Cl⁻, glucose) • serum prolin • renal function (serum creatinine) • (serious) adverse events / reactions including severity of an allergy and prick-test results in case of an anaphylactic/anaphylactoid reaction 
Efficacy:
 
 • hemodynamic measures (heart rate, mean arterial pressure) 
Other:
 
 • demographic data • medical diagnosis leading to intervention • concomitant disease • pre-operative abnormalities • indication for the administration of gelatine solution • hemodynamics and hemodynamic monitoring • concomitant infusions/medication (crystalloids, colloids, blood products, vasoactive drugs) • surgery related data • follow-up (post-operative bleeding complications and renal failure) • final evaluation
Patient population	
 ▪ inclusion criteria 
 • age ≤ 12 years • American Society of Anesthesiologists (ASA) risk score: ≤ III • peri-operative infusion of gelatine solutions

 ▪ exclusion criteria 	
 • informed consent and/or data protection declaration signed by parents/legal guardians (according to local requirements) • inclusion in another investigational study in the field of volume replacement which could interfere with the routine clinical practice regarding the administration of the gelatine solutions 
In addition contraindications as outlined in the valid local Summaries of Product Characteristics (SmPCs) have to be considered.

Observational period per patient	Observation period will start two hours prior first infusion of gelatine solutions and will end two hours after the last gelatine infusion stopped. A follow up will be furthermore recorded at discharge from the hospital or in-hospital 3 months after start of gelatine infusion, whatever occurs first.
Study duration / milestones	60 months after first patient in or termination after treatment of a maximum of 1500 patients, whatever occurs first. Interim analysis should be conducted after enrolment of at least 600 patients.
Sample size	At least 1000 patients and in total a maximum of 1500 patients.

Statistical Analysis and Evaluation

All data will be analyzed by means of tables, figures, listings and statistical tests if appropriate. The final programming will be performed after closure of the database by use of an appropriate statistical software package like SAS or SPSS.

Deviations from the study plan will be assessed as plan violations if at least one of the inclusion or exclusion criteria is not fulfilled. All patients who received the product at least once will be included in the intention-to-treat analysis. All patients who received the product under investigation at least once without any plan violation will be included in the per protocol analysis.

The patient data will be identified by the patient number assigned during data management, the study center, the treatment time and age of patient.

The following statements are valid throughout the statistical analysis:

Variables with metric or ordinal scale will be summarized with

- number of patients (N)
- minimum (Min)
- maximum (Max)
- median (ordinal variables)
- mean (metric variables)
- standard deviation (SD)
- (optional) frequency in the case of ordinal scale (n/%)
- (optional) upper and lower quartile (Q3 and Q1)
- 95% confidence interval of the median/mean
- number of missing data (N_{miss})

Categorical variables will be summarized with

- N
- frequency (n,%)
- N_{miss}

Missing data will be analyzed as such and will not be replaced by estimates.

The following standard procedures for the comparison of subgroups (e.g. study center, country and age) are planned:

- Fisher's exact test for binary data
- χ^2 test for $k \times 2$ tables ($k > 2$)
- U test according to Wilcoxon-Mann-Whitney
- t-test for metric data
- ANOVA (analysis of variance)
- in case of small cell expectations occurring in the majority of the test situations data of ordinal scale will be analyzed by means of the U test instead of the χ^2 test.

All statistical tests will be performed two-tailed with the pre-specified significance level of $\alpha = 5\%$.

An interim analysis will be performed after treatment of at least 600 patients.

The following tables inclusively descriptive statistics (see above) are planned:

- demographic data
- medical diagnosis leading to intervention
- concomitant disease(s)
- pre-operative abnormalities
- indication for and time of administration of gelatine solutions
- gelatine solution application

- dosage in relation to efficacy and safety during different kind of surgeries
- hemodynamic monitoring
- concomitant infusion/medication
- hemodynamic data
- blood gas analysis
- serum proline
- serum creatinine
- surgery related data
- AEs
- ARs
- SAEs / SARs
- follow-up at hospital discharge or in-hospital 3 months after first infusion of gelatine solutions, whatever occurs first
- personal review
- remarks and final conclusion

Where appropriate corresponding figures (e.g. box-plot, bar-chart) will be presented.

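### Heart rate, MAP and serum creatinine depend on age, but the plan pools children up to 12 years and compares subgroups without age bands, change from baseline or age adjustment

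*Combined protocol and SAP*

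**What the plan says.** The Study Overview admits children up to and including 12 years and gives no lower age limit (Patient population). Under Secondary objectives and variables, efficacy consists of "hemodynamic measures (heart rate, mean arterial pressure"), and the safety list includes "renal function (serum creatinine").

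In Statistical Analysis and Evaluation, the summary rules are general: "The following statements are valid throughout the statistical analysis". For metric variables they include "mean (metric variables"), SD, minimum, maximum and a 95% confidence interval. The list of outputs opens with "The following tables inclusively descriptive statistics (see above) are planned", and hemodynamic data and serum creatinine each have an entry. Another entry is "dosage in relation to efficacy and safety during different kind of surgeries".

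On testing, the section states "The following standard procedures for the comparison of subgroups (e.g. study center, country and age) are planned". The methods include "t-test for metric data", the U test and ANOVA, all two-sided at 5%. None takes a covariate as listed.

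The plan names no age bands, age-specific reference, change from the pre-infusion value or age-adjusted model.

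**The concern.** Over the first 12 years of life, normal heart rate falls, normal MAP rises, and creatinine drops after birth and then climbs with muscle mass. This is general paediatric physiology; the documents give no reference values. Three consequences follow if the general rules are applied to measured levels.

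- A mean and SD pooled over the whole age range depend heavily on who was enrolled, and a value abnormal for a child's age can look unremarkable in them.
- A test between age groups will readily find a difference. That difference is real, but it reflects maturation and says nothing by itself about response to the infusion or renal harm.
- Centers, countries and kinds of surgery with different age mixes will differ in these variables even if children of the same age respond identically.

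The study has no comparator, so these summaries and contrasts carry the evaluation of efficacy and renal safety. The primary objective, dosing in routine practice, does not rest on them. The table relating dosage to efficacy and safety by surgery does use them.

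**Working it through.** **What can be reproduced.** The plan gives 1000 to 1500 patients without an effect size, SD, power or precision target, so there is no planned figure to reproduce. The calculations below show what age alone can do. Taken from the plan: N = 1000, two-sided 5%, at least 10 centers. Everything else is assumed and shown as a range.

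**1. Share of variance due to age.** Assumed bands are newborn, infant, 1-5 years and 6-12 years, with shares w = 15/30/30/25%. With band means μ and within-band SD s:

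between-band variance V = Σ w(μ − μ̄)²; share = V / (V + s²).

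| Variable | Band means | s | V | Share |
|---|---|---|---|---|
| Heart rate, narrow | 130/125/110/95 | 15 | 169.7 | 169.7/394.7 = 43% |
| Heart rate, wide | 145/135/110/85 | 15 | 485.3 | 485.3/710.3 = 68% |
| MAP, narrow | 48/52/58/63 | 10 | 27.8 | 27.8/127.8 = 22% |
| MAP, wide | 42/50/62/72 | 10 | 111.4 | 111.4/211.4 = 53% |

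A four-group ANOVA by age has noncentrality N·V/s². In the weakest case (MAP, narrow) this is 27.8 at N = 100, giving power 0.996. At N = 1000 power is 1.00 throughout.

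**2. Two kinds of surgery with contrasting age mixes.** Mix A is 25/45/20/10%, mix B is 5/15/35/45%, and band means are the same in both.

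| Variable | Mean, A | Mean, B | Difference |
|---|---|---|---|
| Heart rate, narrow | 120.25 | 106.50 | 13.75 bpm |
| Heart rate, wide | 127.50 | 104.25 | 23.25 bpm |
| MAP, narrow | 53.30 | 58.85 | 5.55 mmHg |
| MAP, wide | 52.60 | 63.70 | 11.10 mmHg |

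**3. A weaker, unit-free assumption.** Take only a younger and an older group whose levels differ by d within-age SDs.

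*Age comparison, N = 1000.* The smallest gap found with 80% power is (1.960 + 0.842)·√(1/n₁ + 1/n₂). This is 0.18 SD for a 50:50 split, 0.22 for 20:80 and 0.30 for 10:90. A gap of 0.5 SD is found with power of at least 99.7% in all three.

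*Country comparison, 500 against 500, no true country effect.* The younger share is 30% in one country and 30% + m in the other. The spurious difference is m·d. For m = 0.2 and d = 1 it is 0.20 SD, with standard error √[(1 + 0.3·0.7 + 1 + 0.5·0.5)/500] = 0.070. So z = 2.85, and the rejection probability is Φ(2.85 − 1.96) = 81%. Simulation (2000 runs per cell) gives 82% there, and overall:

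| Difference in age mix | d = 0.5 | d = 1 | d = 2 |
|---|---|---|---|
| 0 points | 5% | 5% | 5% |
| 10 points | 12% | 31% | 64% |
| 20 points | 34% | 82% | 99.5% |
| 30 points | 64% | 99% | 100% |

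With the age group in a linear model, rejection is 4.1% to 5.3% in every cell. That is the best case, because the model there holds exactly the age grouping that drives the outcome.

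*Ten centers of 100, younger share from 10% to 50%.* Unadjusted ANOVA rejects in 22%, 74% and 99.5% of runs for d = 0.5, 1 and 2.

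**4. Pooled SD.** With a 50:50 mix the SD is inflated by √(1 + 0.25d²), which is 1.03, 1.12 and 1.41.

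No calculation was made for creatinine.

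**The case against.** The strongest reply is that the plan never says these variables will be analysed as raw levels. The rules are generic and would apply equally to changes. Observation starts two hours before the first infusion, so a baseline may exist. Tests are to be done only where suitable, the three subgroup factors are given as examples, and no test is tied to these variables by name. All of this stands, and it is why the point says what can happen. It does not remove the point: no other scale is named, no criterion for suitability is given, age is one of just three factors mentioned, and the pooled summaries are planned whether or not anything is tested.

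Several stronger readings are tempting but not supported:

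- A reader might infer that every planned comparison is biased by age mix. Center and country contrasts are distorted only where age mix differs; with equal mix the rejection rate stays at 5%. A difference between age groups is not biased at all, only open to misreading.
- A reader might infer that kinds of surgery will be formally tested. Surgery appears only in a planned table and is not among the named subgroup factors.
- A reader might infer that abnormal values will be lost. Listings are planned, patient data carry age, and adverse events and renal failure at follow-up are recorded separately. Still, none of these flags a level as abnormal for age.
- A reader might take the figures as forecasts. They rest on assumed band means, SDs and deliberately contrasting mixes, and they concern levels, whereas response to volume is naturally a change.

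**Conclusion.** The point holds as a conditional one. Followed as written, the plan has no means of separating maturation from response or renal harm in heart rate, MAP and creatinine, and none of separating age mix from center, country or surgery differences. Under the stated assumptions, age accounts for 43 to 68% of heart-rate variance and 22 to 53% of MAP variance. Two contrasting age mixes differ by 14 to 23 bpm and 6 to 11 mmHg. Even a modest 0.5 SD age gap with a 20-point difference in mix raises false rejection between two countries from 5% to 34%. For creatinine the direction of the argument is the same but its size is not established.

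This affects secondary efficacy and safety conclusions in a largely descriptive cohort, not the dosing description itself. It deserves correction because age is already recorded and the remedy is cheap.

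**What to change.** Add to Statistical Analysis and Evaluation:

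1. Define age bands in advance (for example newborn, infant, 1-5 years, 6-12 years) and present heart rate, MAP and serum creatinine within bands.
2. Adjust center and country comparisons of these variables for age, and any comparison by kind of surgery likewise. State the form of the age term; it should be flexible enough for the steep early changes.
3. Where pre-infusion values are recorded, analyse within-patient change from that value, also shown by age band because the size of a change may itself vary with age.
4. State that differences in raw levels between age groups will not be interpreted as differences in efficacy or safety.
5. Optionally, report n (%) outside an age-specific range from one named reference, noting that references from awake children fit anaesthetised children imperfectly.

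The cost is a few sentences, more tables, thinner data per band and some derived variables. No new data need be collected.

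### Centre and country comparisons name no adjustment for age, ASA class or kind of surgery, so any difference found could not be separated from patient mix

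*Combined protocol and SAP*

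**What the plan says.** The section Statistical Analysis and Evaluation announces: "The following standard procedures for the comparison of subgroups (e.g. study center, country and age) are planned". The methods that follow include "Fisher's exact test for binary data", "U test according to Wilcoxon-Mann-Whitney", "t-test for metric data" and "ANOVA (analysis of variance)", plus a chi-square test for larger tables. On the level, it says "All statistical tests will be performed two-tailed with the pre-specified significance level of" 5%.

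No regression model, covariate, stratified test or other case-mix adjustment appears anywhere in the documents. Age enters only as a subgroup factor in its own right. Kind of surgery enters only through a planned descriptive table relating dosage to efficacy and safety.

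The Study Overview describes an observational cohort at "≥ 10 European centers (e.g., Austria, France, Germany, Italy)". Eligible children are up to 12 years old with an ASA score up to III. The efficacy variables are "hemodynamic measures (heart rate, mean arterial pressure)", and serum creatinine is among the safety variables. The plan does not say which outcomes will be compared between centres or countries, or how a difference would be interpreted.

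**The concern.** Nothing in an observational design balances who is treated where. Heart rate, mean arterial pressure and creatinine all change with age in childhood. A site treating mainly infants would therefore differ on these measures from one treating mainly school-age children, even if both managed their patients identically. By listing age as a comparison factor the plan allows that outcomes may vary with age, but it does not carry age into the centre and country tests.

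What is at stake is how these site contrasts can be read. A significant result could reflect practice, patient mix or both. A non-significant one could hide a real difference that patient mix happens to offset. The descriptive primary objective, dosing in routine use, is not affected.

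**Working it through.** The plan gives no effect size, SD or event rate for these comparisons, so there is no figure of its own to reproduce. The size of the problem can only be illustrated. From the documents: two-sided 5% level, ages 0 to 12 years, at least 10 centres, 1000 to 1500 patients. Everything else below is assumed.

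**Two countries, heart rate, no country effect beyond age.** Assumptions: 300 children per country, residual SD 15 bpm, within-country age SD 3 years, heart rate falling b bpm per year, mean ages differing by g years.

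- SD of heart rate within a country: √(15² + 3²b²)
- SE of the difference: SD × √(2/300)
- z = b·g / SE
- Chance of p < 0.05: Φ(z − 1.96) + Φ(−z − 1.96)

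| b (bpm/year) | g (years) | SD | SE | z | Chance of p < 0.05 |
|---|---|---|---|---|---|
| 2 | 1 | √261 = 16.16 | 1.319 | 1.516 | 33% |
| 5 | 1 | √450 = 21.21 | 1.732 | 2.887 | 82% |
| 2 | 0.5 | 16.16 | 1.319 | 0.758 | 12% |
| 5 | 0.5 | 21.21 | 1.732 | 1.443 | 30% |

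Simulation under the same assumptions agrees within simulation error. Adding age as a covariate brought every scenario back to 4.6% to 5.4%.

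**Masking.** Suppose a true country difference of 4 bpm and a 1-year age gap acting in the opposite direction. The crude difference is 4 − 2 = 2 bpm (b = 2) or 4 − 5 = −1 bpm (b = 5). The unadjusted test is then significant in about 33% or 9% of studies, and for b = 5 the crude difference has the wrong sign. With age in the model, the SE is 15 × √(2/300) × √(9.25/9) = 1.242, so z = 4/1.242 = 3.22 and the chance is about 90%.

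**A second set-up: two patient strata.** The strata (younger and older, or two kinds of surgery) differ by D within-stratum SDs. Two centres have shares p and 1 − p in one stratum. The difference in means is D(2p − 1), and the variance per child is 1 + D²p(1 − p).

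- D = 1, 60% v 40%, 100 per centre: difference 0.2, SE √(2 × 1.24/100) = 0.157, z = 1.27, chance 25%. With 150 per centre: 34%.
- D = 1, 70% v 30%: 73% (100 per centre) to 88% (150 per centre).
- D = 0.5, 60% v 40%: 11% to 13%.
- Equal mix: 5%.

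**Ten centres, one-way ANOVA, no centre effect beyond stratum** (2000 simulated studies per scenario). With the logit of the stratum share varying between centres (SD 0.4 to 0.8) and D from 0.5 to 1.5, the unadjusted test is significant in 12% to 97% of studies at 100 per centre and 18% to 99% at 150 per centre. With stratum in the model it is 4% to 6% throughout.

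**Binary outcome.** Assume event rates of 15% and 5% in the two strata. A 70/30 mix gives centre rates of 0.7 × 15% + 0.3 × 5% = 12% against 8%, and a chance of significance of 15% to 21%. A 60/40 mix gives 11% against 9%, and 7% to 8%.

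**The case against.** Several points on the other side stand.

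- A reader might infer that centres will differ in mix and that the differences will be reported as differences in practice, efficacy or safety. The documents say neither. A difference in mix is a reasonable expectation from the design, not a stated fact, and the plan gives no rule for interpreting a site contrast.
- The percentages above might be read as an inflated type I error rate. They are not that. When mean ages differ, the crude means really do differ, and the test detects this correctly. The error would lie in attributing the difference to the site.
- It is tempting to call these contrasts the plan's only look at variation in practice. The plan also tabulates dosage by kind of surgery, gelatine application, indication and concomitant infusions. No stated objective concerns centre or country differences, and tests are to be run only where appropriate.
- It is also tempting to say that absolute doses would be compared between children of different size. The documents do not say how dose is expressed, and they do not name weight as a variable.
- ANOVA can hold more than one factor. None is named, so the plan is underspecified here rather than committed to a one-way analysis.
- Adjustment for kind of surgery relies on extrapolation where centres specialise.

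These points narrow the concern but do not remove it. The condition on testing comes with no criterion and no alternative method. Separate tables of demographics and surgery data do not adjust a p-value. A multi-factor ANOVA would help only if its factors were specified.

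**Conclusion.** The concern holds in a limited form. The plan names centre and country comparisons, and names tests for them without any adjustment for age, ASA class or kind of surgery. If patient mix differs between sites, a significant difference in an age-dependent outcome cannot be separated from case mix, and a real difference could be masked.

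The size cannot be computed from the documents. Under the assumed heart-rate inputs, a 1-year gap in mean age gives about 33% to 82% significant results with no country effect beyond age, and a half-year gap about 12% to 30%. Where the mix is similar the figure stays near 5%, and for the less common binary outcome illustrated it is much lower than for strongly age-dependent metric outcomes. The comparisons are secondary to the plan's aims, so this is a cheap improvement rather than a threat to the study.

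**What to change.** Add to the subgroup paragraph of Statistical Analysis and Evaluation:

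- **Metric outcomes compared between centres or countries:** report a linear model (ANCOVA) with site, age (in bands or non-linear) and ASA class, adding kind of surgery where sites overlap. Show it alongside the unadjusted result.
- **Binary outcomes with enough events:** use the logistic equivalent.
- **Rare events:** show age- and surgery-stratified tables instead of relying on a pooled test.
- **All unadjusted centre and country comparisons:** label them descriptive and not attributable to site practice.

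The cost is SAP wording and modest programming. Age and surgery data are already planned, and ASA class is needed for eligibility. There are two downsides. Because the plan does not replace missing values, patients lacking a covariate drop out of the adjusted model, so the number analysed should be shown. Adjustment for surgery is limited where centres specialise, and the report should say so where that occurs.
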